APPENDIX A. INFORMATION REGARDING EFFECTIVENESS OF CONTRACEPTIVE METHODS

For Subjects Participating in the Study:

The following methods that can achieve a failure rate of less than 1% per year when used consistently and correctly are considered as highly effective birth control methods.

Such methods include:

- Combined (estrogen and progestogen containing) hormonal contraception associated with inhibition of ovulation¹
 - oral
 - intravaginal
 - transdermal
- Progestogen-only hormonal contraception associated with inhibition of ovulation¹
 - oral
 - injectable
 - implantable²
- Intrauterine device (IUD)²
- Intrauterine hormone-releasing system (IUS)²
- Bilateral tubal occlusion²
- Vasectomised partner^{2,3}
- Sexual abstinence⁴

¹ Hormonal contraception may be susceptible to interaction with the IMP, which may reduce the efficacy of the contraception method.

² Contraception methods that in the context of this guidance are considered to have low user dependency.

³ Vasectomised partner is a highly effective method provided of avoiding pregnancy that partner is the sole sexual partner of the WOCBP trial participant and that the vasectomised partner has received medical assessment of the surgical success.

⁴ In the context of this guidance, sexual abstinence is considered a highly effective method only if defined as refraining from heterosexual intercourse during the entire period of risk associated with the study treatments. The reliability of sexual abstinence needs to be evaluated in relation to the duration of the clinical trial and the preferred and usual lifestyle of the subject.

Source: [CTFG 2014](#).

APPENDIX B. PROCEDURES AND SUPPORTIVE CARE GUIDELINES FOR SUBJECTS EXHIBITING IMMUNE-RELATED ADVERSE EVENTS

irAE	Supportive Care
Pneumonitis	
For Grade 2 (mild to moderate new symptoms):
 
 • Monitor symptoms daily and consider hospitalization. • Promptly start systemic steroids per institutional standard of care. • Consider adding prophylactic antibiotics for opportunistic infections in the case of prolonged steroid administration. • Reimaging as clinically indicated. • If no improvement within 3 to 5 days, additional work-up should be considered and prompt treatment with IV methylprednisolone should be started. • If still no improvement within 3 to 5 days despite IV methylprednisone, consider starting immunosuppressive therapy (eg, infliximab), after discussing with the medical monitor. 
Caution: Important to rule out sepsis and refer to infliximab label for general guidance before using infliximab.
 
 • Once improving, gradually taper steroids over ≥ 4 weeks and consider prophylactic antibiotics, antifungal, or anti-PCP treatment (refer to current NCCN Guidelines for treatment of cancer-related infections [Category 2B recommendation]). • Consider pulmonary and infectious disease consult. 
For Grade 3 or 4 (severe or new symptoms, new/worsening hypoxia, life threatening):
 
 • Promptly initiate empiric IV methylprednisolone or equivalent. • Carefully monitor subject, and institute medical intervention as appropriate for the management of symptoms. Consider obtaining pulmonary and infectious disease consult. • If no improvement within 3-5 days, additional work-up should be considered and prompt treatment with additional immunosuppressive therapy (eg, infliximab), after discussing with the medical monitor. 
Caution: Rule out sepsis and refer to infliximab label for general guidance before using infliximab.
 
 • Once improving, gradually taper steroids over ≥ 4 weeks and consider prophylactic antibiotics, antifungals, and in particular, anti-PCP treatment (refer to current NCCN Guidelines for treatment of cancer-related infections [Category 2B recommendation]).

irAE	Supportive Care
Diarrhea/colitis	
Note: Subjects should be carefully monitored for signs and symptoms of enterocolitis (such as diarrhea, abdominal pain, blood or mucus in stool, with or without fever) and of bowel perforation (such as peritoneal signs and ileus).
 
For Grade 2 (mild to moderate new symptoms):
 
 • Consider symptomatic treatment, including hydration, electrolyte replacement, dietary changes (eg, American Dietetic Association colitis diet), and loperamide and/or budesonide. • Promptly start systemic steroids per institutional standard of care. • If event is not responsive within 3 to 5 days or worsens, GI consult should be obtained for consideration of further work-up, and prompt treatment with IV methylprednisolone started. • If still no improvement within 3 to 5 days, consider starting immunosuppressives (eg, infliximab) after discussing with the medical monitor. 
Caution: Important to rule out bowel perforation and refer to infliximab label for general guidance before using infliximab.
 
 • Consult medical monitor if no resolution to \leq Grade 1 in 3-4 days. • Once improving, gradually taper steroids over \geq 4 weeks and consider prophylactic antibiotics, antifungals, and anti-PCP treatment (refer to current NCCN Guidelines for treatment of cancer-related infections [Category 2B recommendation]). 
For Grade 3 or 4 (severe or new symptoms, new/worsening diarrhea, life threatening):
 
 • Treatment with systemic corticosteroids should be initiated per institutional standard of care. • Manage symptoms and consider GI consult for further work-up as appropriate. • If still no improvement within 3-5 days, consider starting immunosuppressives (eg, infliximab), after discussing with the medical monitor. 
Caution: Ensure GI consult to rule out bowel perforation and refer to infliximab label for general guidance before using infliximab.
 
 • Once improving, gradually taper steroids over \geq 4 weeks and consider prophylactic antibiotics, antifungals, and anti-PCP treatment (refer to current NCCN Guidelines for treatment of cancer-related infections [Category 2B recommendation]).

irAE	Supportive Care
Hepatitis	
For Grade 2 (mild to moderate new symptoms):
 
 • Observe subject with regular and frequent checking of liver chemistries until improving or resolved. • Rule out non-irAE etiologies. • If event is persistent (> 3-5 days) or worsens, consider starting systemic steroids per institutional standard of care. • If still no improvement within 3-5 days, consider additional work-up and prompt treatment with IV methylprednisolone. • If still no improvement within 3-5 days, consider starting immunosuppressives (eg, mycophenolate mofetil), after discussing with the medical monitor. • Infliximab should NOT be used. • Once improving, gradually taper steroids over ≥ 4 weeks and consider prophylactic antibiotics, antifungals, and anti-PCP treatment (refer to current NCCN Guidelines for treatment of cancer-related infections [Category 2B recommendation]). 
For Grade 3 or 4 (severe or new symptoms, new/worsening hepatitis, life threatening):
 
 • Promptly initiate empiric IV methylprednisolone or equivalent. • If still no improvement within 3 to 5 days, consider starting treatment with immunosuppressive therapy (eg, mycophenolate mofetil), after discussing with the medical monitor. • Infliximab should NOT be used. • Consider hepatology consult for additional work-up, as appropriate. • Once improving, gradually taper steroids over ≥ 4 weeks and consider prophylactic antibiotics, antifungals, and anti-PCP treatment (refer to current NCCN Guidelines for treatment of cancer-related infections [Category 2B recommendation]).

irAE	Supportive Care
Dermatitis	
Note: Monitor subjects for signs and symptoms of dermatitis such as rash and pruritus. Unless an alternate etiology has been identified, signs or symptoms of dermatitis should be considered immune-mediated. If there is any bullous formation, the medical monitor should be contacted, and the study drug should be discontinued.
 
For Grade 2 (mild to moderate new symptoms):
 
 • Consider dermatology consult. • Consider symptomatic treatment per institutional standard of care. • Consider moderate-strength topical steroid. • If no improvement of rash/skin lesions occurs within 3 to 5 days or is worsening despite symptomatic treatment and/or use of moderate strength topical steroid, discuss with medical monitor and promptly start systemic steroids. 
For Grade 3 or 4 (severe or new symptoms, new/worsening dermatitis, life threatening):
 
 • Consider dermatology consult. • Promptly initiate empiric IV methylprednisolone or equivalent. • Carefully monitor subject, and institute medical intervention as appropriate for the management of symptoms. • Consider hospitalization. • Once improving, gradually taper steroids over ≥ 4 weeks and consider prophylactic antibiotics, antifungals, and anti-PCP treatment (refer to current NCCN Guidelines for treatment of cancer-related infections [Category 2B recommendation]). • Discuss with medical monitor.
Renal failure or nephritis	
Note: Subjects should be monitored for signs and symptoms that may be related to changes in renal function. Subjects should be thoroughly evaluated to rule out any alternative etiology. Steroids should be considered in the absence of clear alternative etiology even for low-grade events (Grade 2) in order to prevent potential progression to higher grade event.
 
For Grades 2 to 4:
 
 • Carefully monitor subject, and institute medical intervention as appropriate for the management of symptoms. Consider consult with nephrologist, if clinically indicated. • If event is persistent (> 3-5 days) or worsens, promptly start systemic steroids per institutional standard of care. • If event is not responsive within 3-5 days or worsens despite steroids, additional work-up should be considered, and prompt treatment with IV methylprednisolone started. • Once improving, gradually taper steroids over ≥ 4 weeks and consider prophylactic antibiotics, antifungals, and anti-PCP treatment (refer to current NCCN Guidelines for treatment of cancer-related infections [Category 2B recommendation]).

irAE	Supportive Care
Endocrinopathies	
Note: Subjects should be monitored for clinical signs and symptoms of hypophysitis, adrenal insufficiency (including adrenal crisis), and hyper- or hypothyroidism. Subjects may report fatigue, headache, mental status changes, abdominal pain, unusual bowel habits, and hypotension or report nonspecific symptoms that may resemble other causes, such as brain metastasis or underlying disease. Unless an alternate etiology has been identified, signs or symptoms of endocrinopathies should be considered immune-mediated.
 
For Grade 2 (mild to moderate new symptoms):
 
 • In hypophysitis, treat with systemic corticosteroids, per institutional standard of care. When symptoms improve to Grade 1 or less, steroid taper should be started and continued over no less than 4 weeks. Replacement of appropriate hormones may be required as the steroid dose is tapered. 
Note: These suggested supportive care measures also apply to Grade 3 hypophysitis
 
 • In hyperthyroidism, nonselective beta-blockers (eg, propranolol) are suggested as initial therapy. • In hypothyroidism, thyroid hormone replacement therapy, with levothyroxine or liothyronine, is indicated per standard of care. 
Note: Isolated hypothyroidism may be treated with replacement therapy without treatment interruption and without corticosteroids.
 
 • Evaluate endocrine function and, as clinically indicated, consider pituitary scan. • For subjects with abnormal endocrine work-up, except for those with isolated hypothyroidism, consider short-term, high-dose corticosteroids (eg, methylprednisolone or IV equivalent), and initiate appropriate hormone replacement therapy. • For subjects with normal endocrine work-up (laboratory assessments or MRI), repeat laboratory assessments/MRI as clinically indicated. • For Grade 3 or 4 (severe or new symptoms, new/worsening endocrinopathies, life threatening): • Hypothyroidism may be treated with replacement therapy without treatment interruption and without corticosteroids. • In hyperthyroidism, treat with an initial dose of IV corticosteroid followed by oral corticosteroids. Consider initiation of systemic corticosteroids at a dose of 1-2 mg/kg per day of prednisone or equivalent, and initiate appropriate hormone replacement therapy. Once improving, gradually taper immunosuppressive steroids over ≥ 4 weeks. • In hypophysitis, treat with an initial dose of IV corticosteroids followed by oral corticosteroids. When symptoms improve to Grade 1 or less, steroid taper should be started and continued over no less than 4 weeks. Replacement of appropriate hormones may be required as the steroid dose is tapered. • For adrenal crisis, severe dehydration, hypotension, or shock: immediately initiate IV corticosteroids with mineralocorticoid activity. • Consult endocrinologist. • Consult medical monitor.

irAE	Supportive Care
Neuropathies	
Note: Monitor subjects for symptoms of motor or sensory neuropathy such as unilateral or bilateral weakness, sensory alterations, or paresthesia.
 
For Grade 2 (mild to moderate new symptoms):
 
• Consider systemic corticosteroids per institutional standard of care in addition to appropriate symptomatic treatment.• If no improvement within 3-5 days, consider additional work-up and consider treating with additional immunosuppressive therapy (eg, IV IgG), after discussing with the medical monitor. 
For Grade 3 or 4 (severe or new symptoms, new/worsening neuropathies, life threatening):
 
• Consider initiation of systemic corticosteroids (IV administration should be strongly considered) for severe neuropathies.• Institute medical intervention as appropriate for management of severe neuropathy.• If no improvement within 3-5 days despite IV corticosteroids, consider additional workup and consider treating with additional immunosuppressants (eg, IV IgG) after discussing with the medical monitor.• Once stable, gradually taper steroids over ≥ 4 weeks.

GI = gastrointestinal; IgG = immunoglobulin G; irAE = immune-related adverse event; IV = intravenous; MRI = magnetic resonance imaging; NCCN = National Comprehensive Cancer Network; PCP = pneumocystis pneumonia.

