5.4.6. Criteria and Procedures for Dose Interruptions and Adjustments of Study Drug

Treatment with study drug may be delayed to allow for resolution of toxicity. Subjects may resume treatment if no medical condition or other circumstance exists that, in the opinion of the investigator, would make the subject unsuitable for further participation in the study. For toxicities that occur outside of the 28-day DLT period, the treating investigator should contact the medical monitor to discuss the case of any subject whose treatment has been delayed for more than 4 weeks (28 days) before restarting treatment with study drug.

Instructions for dose modifications and interruptions are outlined in [Table 4](#). Individual decisions regarding dose interruptions and reductions should be made using appropriate clinical judgment in consultation with the medical monitor, taking into account relatedness of the AE to the study drug and the subject's underlying condition. Adverse events that have a clear alternative explanation, or transient (≤ 72 hours) abnormal laboratory values without associated clinically significant signs or symptoms, may be exempt from dose-reduction rules. Dose interruptions are permitted in the case of medical/surgical events or logistical reasons not related to study therapy (eg, elective surgery, unrelated medical events, subject vacation, holidays). Subjects should be placed back on study therapy within 4 weeks (28 days) of the scheduled interruption, unless otherwise discussed with the sponsor. The reason for interruption should be documented in the subject's study record.

Table 4: Rules for Interruption and Restarting of Study Drug

CTCAE Grade or Severity	Timing for Restarting Treatment	Dose Level for Restarting Treatment	Treatment Discontinuation ^a
1-2 (mild-moderate)	Continue treatment at the discretion of the investigator.	N/A	N/A
3 (severe)	Toxicity resolves to Grade 0-1.	Reduce by 1 dose level. ^b	Toxicity does not resolve within 4 weeks (28 days) of last dose, except by approval of the medical monitor. OR Second occurrence of previously resolved Grade 3 AE.
4 (life-threatening)	Permanently discontinue.	N/A	Permanently discontinue.

^a Permanently discontinue for any severe or Grade 3 AE that recurs or any life-threatening event.

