5.4.9. Criteria for Permanent Discontinuation of Study Drug

The occurrence of unacceptable toxicity not caused by the underlying malignancy will be presumed to be related to study drug treatment and will require that the study drug be permanently discontinued. Unacceptable toxicity is defined as follows:

- Grade 4 or life-threatening AEs (see [Table 4](#) and [Table 6](#)).
- \geq Grade 2 ocular irAE.
- Occurrence of an AE that is related to treatment with the study drug that, in the judgment of the investigator or the sponsor's medical monitor, compromises the subject's ability to continue study-specific procedures or is considered to not be in the subject's best interest.
- An AE requiring more than 2 dose reductions of study drug, or more than 1 dose reduction if the starting dose is 7 mg (see [Table 2](#)).
- Persistent AE requiring a delay of therapy for more than 4 weeks (28 days), unless a greater delay has been approved by the sponsor.

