5.5. Withdrawal of Subjects From Study Treatment

5.5.1. Withdrawal Criteria

A subject may choose to withdraw from the study at any time or be withdrawn by the investigator or sponsor, if the subject is noncompliant with the study requirements. Subjects may also be withdrawn at the discretion of the FDA or health authorities. If a subject is withdrawn, then every reasonable effort should be made to determine the reason for withdrawal, and this information should be recorded in the electronic case report form (eCRF).

Subjects **must** be withdrawn from **study drug** for the following reasons:

- The subject becomes pregnant.
- Consent is withdrawn. Subjects may choose to withdraw from the study at any time without penalty of jeopardizing their health care or loss of benefits to which the subject is otherwise entitled.
- Further participation would be injurious to the subject's health or well-being, in the investigator's medical judgment.
- The subject is lost to follow-up.

- Unacceptable toxicity (see [Section 5.4](#)). Subjects with unacceptable toxicities must be withdrawn from study drug but will continue to be followed during the safety follow-up visits as specified in [Section 6.4](#).
- The study is terminated by the sponsor.
- The study is terminated by the local health authority, IRB, or IEC.

A subject **may** be discontinued from study treatment as follows:

- Confirmed radiographic progression of disease per mRECIST v1.1. See [Section 7.7.1](#).

Note: For unconfirmed progression, see [Section 7.7.1](#).

Note: A subject may be granted an exception to continue on treatment with confirmed radiographic progression if clinically stable or clinically improved. See [Section 7.7.1](#).

- If, during the course of the study, a subject is found not to have met eligibility criteria (see [Section 3](#)), then the medical monitor, in collaboration with the investigator, will determine whether the subject should be withdrawn from the study.
- If a subject is noncompliant with study procedures or study drug administration in the investigator's opinion, then the sponsor should be consulted for instruction on handling the subject.

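### Appendix B allows hypothyroidism under its Grade 3 or 4 heading to be treated without interrupting study drug and does not exclude Grade 4, against the mandatory Grade 4 stop in Table 4, 5.4.9 and 5.5.1

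*Protocol*

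**What the plan says.** **Appendix B, Endocrinopathies.** The relevant list is headed "For Grade 3 or 4 (severe or new symptoms, new/worsening endocrinopathies, life threatening". Its first item says that "hypothyroidism may be treated with replacement therapy without treatment interruption and without corticosteroids". The list ends by telling the site to consult an endocrinologist and the medical monitor. The Grade 2 part of the same row has a near-identical note, but restricted to isolated hypothyroidism.

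**Section 5.4.6, Table 4.** This section names Table 4 as the source of dose modification and interruption instructions. At Grade 4 the action is permanent discontinuation, and footnote a reads "Permanently discontinue for any severe or Grade 3 AE that recurs or any life-threatening event". At Grade 3, dosing restarts only after resolution to Grade 0-1 and at one dose level lower. One ground for stopping at Grade 3 is "Toxicity does not resolve within 4 weeks (28 days) of last dose, except by approval of the medical monitor".

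**Section 5.4.9.** "The occurrence of unacceptable toxicity not caused by the underlying malignancy will be presumed to be related to study drug treatment", and permanent discontinuation is then required. The first criterion listed is "Grade 4 or life-threatening AEs".

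**Section 5.5.1.** "Subjects with unacceptable toxicities must be withdrawn from study drug", by reference to Section 5.4.

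**Table 5, Grade 3-4 row.** Study drug should be stopped for good for irAEs that are severe or clinically significant. The table footnote, like Section 5.4.7, refers the site to Appendix B for specific irAEs.

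**The concern.** A site managing an immune-related event is directed to Appendix B for the specific condition. For hypothyroidism, the text it finds under the Grade 3 or 4 heading allows dosing to go on. If the event is Grade 4, a site acting on that line would keep dosing a subject whom Sections 5.4.9 and 5.5.1 require to come off study drug, and could believe that it was following the protocol.

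What is at stake is subject safety and protocol compliance in an uncommon situation. The statistical design is not touched. Table 3 already counts a Grade 4 irAE as a DLT regardless of duration, so the DLT tally within the 28-day window does not depend on which text a site follows.

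**Working it through.** No arithmetic applies and the plan states no figure to reproduce. The check is a comparison of the texts.

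| Place | Grade 4 | Grade 3 | Endocrine exception |
|---|---|---|---|
| Appendix B, hypothyroidism item | No interruption needed | No interruption needed | This is the permission itself |
| Table 4 and footnote a | Permanent discontinuation | Hold to Grade 0-1, then one level lower | None |
| Section 5.4.9 | Permanent discontinuation | Not listed by grade | None |
| Section 5.5.1 | Withdrawal from study drug, through Section 5.4 | Only if the toxicity is unacceptable under Section 5.4 | None |
| Table 5 | Permanent discontinuation if severe or clinically significant | Same | None |

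**Step 1: is Grade 4 inside the permission?** Yes. The heading names Grade 4 and life-threatening events, and the item carries no grade limit of its own. The same row does separate grades elsewhere: a note extends the Grade 2 measures for hypophysitis to Grade 3 only. A Grade 3 limit for hypothyroidism could have been written in the same way.

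**Step 2: does the permission widen with severity?** Yes. At Grade 2 it is limited to isolated hypothyroidism; at Grade 3 or 4 that limit is gone. This looks like a drafting slip.

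**Step 3: does any discretion waive the Grade 4 stop?** No.
- The medical monitor's approval in Table 4 sits in the Grade 3 row only.
- Section 5.4.6 says "Individual decisions regarding dose interruptions and reductions should be made using appropriate clinical judgment in consultation with the medical monitor". That covers interruptions and reductions.
- The exemptions named in 5.4.6 are for AEs with a clear alternative explanation and for transient laboratory values. They are exemptions from the dose-reduction rules, not from permanent discontinuation.
- The Appendix B instruction to consult the medical monitor gives no authority to override the stop.

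**Step 4: what about Grade 3?** Read literally, the item also departs from the Table 4 Grade 3 row, which requires a hold and a reduction, and sits badly with Table 5. Clinical judgment under 5.4.6 softens this departure, so it is weaker than the one at Grade 4. It matters mainly for the repair: keeping the option at Grade 3 without touching the tables would leave an inconsistency in the text.

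**The case against.** **The protocol already says which text governs.** Table 4 is named as the source of dosing instructions, Appendix B is supportive-care guidance, the measures are described as suggested, and the item is permissive. Against it stand three mandatory stops. Most of this stands. A reader might infer that the protocol leaves the question entirely open because it has no precedence clause; the 5.4.6 reference to Table 4 does not support that. The stop should prevail. What remains is wording that tells the site the opposite at the place where it is sent to look.

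**Waiving an interruption need not waive a discontinuation.** On this reading the Appendix B item removes a temporary hold and leaves the Grade 4 stop alone. This is strained. A drug that has been stopped permanently cannot sensibly be described as continuing without interruption, and a site would read the line as leave to carry on dosing.

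**There are safeguards on the route.** Table 5 tells the site to discontinue for severe or clinically significant irAEs before its footnote points to Appendix B, and the Appendix B list ends with two consultations. This stands. It lowers the chance of an error without removing the contradiction.

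**The hypothyroidism item is not the only study-drug instruction in Appendix B.** Correct. The Grade 2 note on isolated hypothyroidism is another, and the general dermatitis note calls for discontinuation if there is bullous formation. The point does not depend on the item being unique.

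**Conclusion.** The contradiction at Grade 4 is real and rests on the text alone, taking treatment interruption to mean interruption of study drug, which is its natural sense beside replacement therapy and corticosteroids. It is narrow: one item in one row of Appendix B, with mandatory rules elsewhere that should win. The Grade 3 mismatch is secondary.

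No size can be put on it. The documents give no frequency for Grade 4 hypothyroidism, and the event is probably rare. A reader might infer an exposure figure from Table 8: endocrine tests fall on Day 1 of odd cycles from Cycle 3, so 2 × 14 = 28 days apart, and 28 / 14 = 2 infusions would be given from one test to the next. The documents do not support that as the consequence. The conflict bites only once the event has been recognised, and the test interval does not govern what happens after that. AEs are assessed on Day 1 of every cycle (Table 7), laboratory results must be acceptable before each new cycle (Section 7.6.5), and the Appendix B list calls for consultation.

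This should be corrected because it concerns a subject-safety rule and is cheap to mend. It does not threaten the design or the analysis.

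**What to change.** 1. In the Grade 3 or 4 part of the Endocrinopathies row, add: *For Grade 4 or life-threatening hypothyroidism, permanently discontinue study drug (Table 4, Sections 5.4.9 and 5.5.1).* Limit the no-interruption sentence to isolated Grade 3 hypothyroidism, in consultation with the medical monitor.
2. If the Grade 3 option is kept, add a matching explicit exception to the Table 4 Grade 3 row and to Table 5. If it is not wanted, delete it so that Grade 3 follows Table 4.

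The second step is needed. Limiting the sentence to Grade 3 alone would leave Appendix B at odds with the Grade 3 hold-and-reduce rule and with Table 5.

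The cost is about two sentences in Appendix B and, if the option stays, a short exception in each of two tables at the next amendment. Design, visits, data collection and sample size do not change.
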